6.2. Preparation/Handling/Storage/Accountability

6.2.1. Acquisition

AV7909 and BioThrax liquid suspension for injection and saline placebo will be shipped to investigational sites from the drug depot following approval by the institutional review board/independent ethics committee (IRB/IEC) and Emergent. All AV7909 and BioThrax shipments will be accompanied by TempTale® temperature monitors to record any excursions outside of required storage conditions of 2-8 °C (36-46 °F). Detailed instructions for inventory receipt, temperature excursions, and IP resupply are provided in the Pharmacy Manual.

6.2.2. Product Storage and Stability

Investigational products will be secured and accessible only by unblinded study personnel authorized by the PI. AV7909 and BioThrax will be stored at the investigational site in a

designated, restricted-access refrigerator maintained within the required storage conditions of 2-8 °C (36-46 °F). The vials will not be frozen. In order to guarantee proper storage conditions, the minimum, actual and maximum temperature in the storage refrigerator will be continuously monitored for correct temperature. A back-up power source for the refrigerator is required.

Investigational products that are suspected of loss of cold chain, whether during shipping or at the investigational site, will be immediately quarantined and not used until further notice. The site will refer to the Pharmacy Manual and contact the unblinded contract research organization (CRO) study monitor for further instruction.

After a single dose is withdrawn from either AV7909 or BioThrax vials for administration to a participant, the vial will thereafter be maintained at room temperature pending final drug accountability procedures.

Saline placebo is to be stored at room temperature (20-25 °C; 68-77 °F) before and after use.

6.2.3. Preparation of Investigational Product for Injection

Vaccine doses must not be drawn into a syringe until immediately before administration. Pre-filling of the syringes is discouraged because of the potential for administration errors. In addition, the stability of the vaccine stored in the syringes has not been determined. An unblinded study pharmacist or other designated, licensed study personnel will prepare each syringe of vaccine or placebo according to the following instructions in a segregated area of the clinical site ensuring the IP prepared for administration is kept apart from blinded site personnel:

1. A separate 1”- or 1½” 23- or 25-gauge sterile needle and 1.0 mL syringe will be used for each participant.
2. The IP (AV7909, BioThrax, and placebo) will be gently rolled between the hands to ensure that the suspension is homogeneous and visually inspected for particulate matter and discoloration prior to preparing the syringe. If the product appears discolored or has visible particulate matter, the vial must not be used – THE VIAL MUST BE QUARANTINED and retained for collection by the CRO study monitor or Sponsor representative.
3. The rubber stopper will be wiped with an alcohol swab and allowed to air dry before inserting the needle. The IP will be drawn into a sterile 1.0 mL syringe for administration. The volume and contents of the syringe will be verified by a second unblinded person before administration.
4. The syringe barrel will be masked to obscure the contents. This masking must not cover the syringe hub, to allow for observation of any blood return during administration.
5. The vial will be resealed and covered with tamper-evident tape to indicate no additional doses may be withdrawn (applies to the AV7909 and BioThrax multi-dose vials).

6.2.4. Accountability

Authorized, unblinded pharmacy personnel will maintain accurate records of receipt of AV7909, BioThrax, and saline placebo used for the study, including dates of receipt and TempTale records. In addition, accurate records will be kept regarding when and how much of each IP is

dispensed and used for each participant in the study. All accountability procedures will be maintained throughout the duration of the study, as detailed in the Pharmacy Manual.

No vials of AV7909, BioThrax, or saline placebo, including empty, damaged or partially used ones, are to be discarded by the investigator site. Once vaccinations are completed, in order to satisfy regulatory requirements regarding drug accountability, the unblinded CRO study monitor will reconcile all vials of study product, used and unused, according to applicable state and federal regulations and destroy per Emergent instructions.

6.3. Measures to Minimize Bias

6.3.1. Method of Treatment Assignment

After the ICF has been signed and dated by the participant and PI/designee but before any screening procedures are performed, the participant will be assigned a unique subject identification (ID) number by the site. To maintain confidentiality, the subject ID will be used to identify the participant for data collected in eCRFs throughout the trial and for all clinical laboratory samples. The investigational site will retain a master list linking the subject ID with the name, date of birth, and contact information of the participant. The master list is to be retained by the site only and is not to be collected by Emergent or its agents.

If a participant is rescreened, a new subject ID will be assigned. To link records to the same participant, the participant's previous subject ID will be recorded in the eCRF along with the new subject ID.

At the Day 1 (randomization) visit, after the PI has confirmed that the participant meets all of the inclusion criteria and none of the exclusion criteria, the participant will be randomized to a treatment group via an interactive voice and/or web response system (IxRS). The randomization plan will describe the method of treatment allocation and implementation of this method in the IxRS. This plan will be prepared by a statistician and finalized prior to randomization of the first participant. Randomization will be stratified by site.

If a participant signs an ICF but is never randomized, the participant is considered to be a screen failure (refer to [Section 5.4](#)).

Randomized participants who withdraw from the study for any reason will not be replaced in this trial.

6.3.2. Blinding

The site pharmacists or other designated, licensed study personnel who will prepare and/or administer the vaccinations will be unblinded to IP assignment. These individuals must be licensed to administer medication/vaccination and will not be involved with participant evaluations, nor will they engage in other study activities that could reveal the blind or introduce bias in the study data.

Principal investigators (PIs), all investigational site staff (except those responsible for preparing/administering the IP), representatives of the Sponsor (except unblinded study monitor[s] and unblinded Quality Assurance representative[s]), representatives of Biomedical Advanced Research and Development Authority (BARDA), CRO staff (except unblinded

statistician and unblinded study monitor[s]), and all participants enrolled in this study will be blinded to the IP assignment. To facilitate study oversight while preserving the study blind, a minimum number of CRO and Sponsor personnel will have access to treatment randomization information. The unblinded CRO statistician will have access to the treatment assignment information in the IxRS to support the activities of the DSMB. During monitoring visits, an unblinded CRO study monitor will check that the blind has been maintained properly and will review IP accountability records. Oversight of this activity will be facilitated by the Sponsor's unblinded study monitor(s). Blinded CRO study monitors will continuously assess the progress of the study, but not have access to the unblinded pharmacy records. Individuals with access to the treatment assignment details will not share the identifying information with blinded personnel while the study blind is in effect.

Under certain circumstances (eg, safety reasons, required reporting to regulatory agencies), unblinding of IP for a particular participant will be allowed. Otherwise, unblinding of the study will only occur after the clinical database has been locked. Refer to [Section 9.5](#) for procedures on how to break the blind for individual participants or procedures in case of accidental participant unblinding. Refer to the Pharmacy Manual for procedures in case of accidental unblinding of study-affiliated personnel (Sponsor, CRO, BARDA).

6.4. Treatment Compliance

The IP will be administered to the subject by the unblinded investigational site staff in a controlled, clinical environment. The date and time of the vaccine administration will be recorded on the source documents and eCRF.

6.5. Concomitant Therapy

Medication usage will be collected from participants and recorded in the participant's source documents and eCRF at Screening and at each study visit up through Day 64/EWV. After Day 64, medication usage will be recorded in the eCRF if involving an AE, SAE or AESI. Prior medications are those used from within 30 days before Screening through the time of the first vaccination, while concomitant medications are those used after the first vaccination. The medication name, dose, route, frequency, indication, and stop and start days/times for each new medication will be recorded. Refer to [Section 5.2](#) for prior medication usage that is disqualifying for study participation.

Prohibited and restricted concomitant medications during the study, which include anti-inflammatory or antipyretic medications, vaccines, immunomodulatory agents, antineoplastic agents, and immunoglobulins/other blood products, are summarized in [Table 4](#). The MM should be consulted for any questions about prohibited or restricted medication usage.

Table 4: Prohibited and Restricted Concomitant Medications

Type ^a	Examples ^b
Anti-inflammatory or antipyretic medication: prohibited within 24 hours before or after vaccination	Aspirin-containing medication, NSAIDs, acetaminophen-containing medication
Any commercially-available vaccine through two weeks after the last vaccination	BCG Vaccine, Engerix-B, Havrix, HEPLISAV-B, Imovax, influenza vaccines, Ixiaro, JE-Vax, Menomune-A/C/Y/W-135, Prevnar 13, Recombivax HB, Twinrix, Vaxchora, Vaqta
Immunomodulatory agents through Month 13 Note: inhalation use (eg, for seasonal allergies) is permitted.	Any systemic corticosteroids including, but not limited to, generic and brand names of: betamethasone, budesonide, cortisone acetate, dexamethasone, hydrocortisone, methylprednisolone, prednisolone, prednisone, triamcinolone Azasan (Salix Pharmaceuticals), CellCept (Roche Laboratories), Gengraf (Abbott), MICRhoGAM ultra-filtered (Ortho-Clinical), Myfortic (Novartis), Neoral (Novartis), Orthoclone OKT3 sterile solution (Ortho Biotech), Prograf (Fujisawa), Rapamune (Wyeth), Rituximab (Rituran, Mabthera; Genentech), Sandimmune (Novartis), Simulect (Novartis), Thymoglobulin (SangStat Medical Corp.), Zenapax (Roche Laboratories)
Antineoplastic agents through Month 13	Cyclophosphamides (Cytoxan, Neospar), Cytarabine (Cytosar-U, Ara-C, Cytosine arabinoside), Depocyt (Enzon), methotrexate, vincristine (Oncovin, Vincasar)
Immunoglobulins and/or any blood products through Month 13	Anthrasil, Bivigam, Carimune NF Nanofiltered, CUVITRU, Flebogamma DIF 5% & 10%, GamaSTAN S/D, Gammagard, Gammaplex 5% & 10%, Gamunex-C, HepaGam B, Hizentra, HYQVIA, OCTAGAM, Privigen, VARIZIG
Any investigational or nonregistered product (drug, vaccine, device, or combination product) through Month 13	-

MM=Medical Monitor; NSAID = non-steroidal anti-inflammatory drug.

^aRefer to [Section 5.2](#) for prior medication usage that is disqualifying for study participation.

^bExample medications are provided for reference – this is not meant to be an exhaustive list. Consult with the MM as needed.

The use of pain/fever medications recorded in participant e-diaries will be reviewed by investigational site staff during routine monitoring of e-diary entries (refer to [Section 8.3.5.1](#)) and, for completeness of the concomitant medication record, must also be added to the eCRF.

7. STOPPING RULES, DISCONTINUATION/WITHDRAWAL CRITERIA AND PROCEDURES

7.1. Entire Study

Study enrollment and vaccinations may be temporarily halted by the DSMB or the Sponsor if any of the following occur, pending further evaluation:

- >3% of participants having the same Grade 3 or higher AE
- 3 suspected unexpected serious adverse reactions (SUSARs) within the same body system as assessed by the Sponsor
- 5 potential AESIs considered related to the IP, as assessed by the Sponsor
- single AESI considered related to the IP, as assessed by the DSMB

These events will be reviewed by the DSMB and a recommendation will be made regarding vaccinations, continuation of study, or study termination. The procedures for DSMB notification and review of SUSARs, AESIs, and other significant events will be outlined in the DSMB Charter (refer to [Section 8.4.1](#)).

Emergent, BARDA, the IRB/IEC and/or FDA reserve the right to terminate the study at any time for clinical or administrative reasons. This study may be terminated due to safety concerns, failure to meet expected enrollment goals, administrative reasons or at Emergent's discretion. If the study is terminated prematurely, Emergent will provide written notification to all investigators and regulatory authorities and will specify the reason(s) for early termination. The investigator must inform the IRB/IEC promptly and provide the reason(s) for the termination.

7.2. Individual Site

The CRO will promptly notify Emergent if the trial is terminated by the PI or the IRB/IEC at the site.

A particular site may be terminated from the trial at the discretion of the PI, Emergent, or IRB/IEC, eg, for non-enrollment of participants or non-compliance with the protocol. Emergent may decide to replace a terminated site.

7.3. Individual Subject

All participants have the right to withdraw at any time during the study without prejudice. The PI can also discontinue an individual's participation in the trial at any time if medically necessary or for reasons of noncompliance.

Every attempt will be made to follow participants for safety for the entire duration of the trial through Month 13 providing they have received at least one vaccination. Participants who discontinue treatment prematurely for any reason after receiving the first vaccination will be encouraged to continue in the study for any remaining study visits (for safety assessments only) and the safety follow-up phone calls at Day 43 and Months 4, 7, 10, and 13.

If a participant discontinues vaccinations and/or participation in the study, the reason(s) must be fully evaluated and recorded appropriately in source documents and eCRFs. Reason for discontinuation of vaccination and reason for withdrawal from the study are to be recorded separately on eCRFs. If the participant is being discontinued because of an AE, that AE will be indicated as the reason for vaccination discontinuation and/or study withdrawal.

7.3.1. Discontinuation of Vaccination

Vaccinations will be permanently discontinued in participants who meet the individual participant halting rules in [Table 5](#). The date and reason for discontinuation of vaccination is to be recorded on the eCRF.

Participants who have received at least one vaccination will be encouraged to participate in all remaining study visits (for safety assessments only) and safety follow-up calls through Month 13. A participant who complies with safety-only assessments after prematurely discontinuing vaccinations will be considered to be continuing in the study. Participants who are being followed for safety only will not be required to have any further TNA blood draws and assessments associated with vaccination (eg, vital signs evaluation occurring 30 ± 5 minutes after vaccination and e-diary). However, e-diary entries associated with a past vaccination and site review of those entries must still be completed (refer to [Section 8.3.5.1](#)).

If a participant who has received at least one vaccination discontinues treatment prematurely but refuses to continue with safety-only follow up, the participant must be withdrawn from the study, with the reason for study withdrawal recorded on the eCRF (refer to [Section 7.3.2](#)). If the refusal to participate in safety-only follow-up procedures occurs before Day 64, the participant will be requested to attend an EWV for a final in-clinic safety assessment before being withdrawn from the study (refer to EWV procedures under [Section 8.1.7](#)).

Table 5: Criteria for Discontinuation of Vaccination for Individual Participants

No.	Item
1.	Grade 2 or greater hypersensitivity believed by the PI to be related to the vaccine, eg, anaphylaxis, allergic reaction
2.	Any Grade 3 or higher systemic reactogenicity symptom assessed by e-diary and confirmed by the PI
3.	Any AE that would pose a risk to the participant as determined by the PI if continued vaccinations were to occur
4.	Any violation of eligibility criteria discovered after randomization that would pose a risk to the participant, as determined by the PI and agreed by the MM
5.	Febrile illness (fever > 100.4 °F) within three days prior to any vaccination (Exception: The vaccination visit may be rescheduled to another day outside this three-day period providing it will not fall outside the required visit window for the visit [refer to Section 8.1].)
6.	Receipt of IP associated with loss of cold chain
7.	Suspected or confirmed pregnancy (refer to Section 9.4). (Exception: In the case of suspected pregnancy, if the subsequent serum pregnancy test is negative, the vaccination visit may be rescheduled to another day providing it will not fall outside the required visit window for the visit [refer to Section 8.1].)
8.	Scheduling or other conflict results in a vaccination visit falling outside the required window (± 1 day for Day 15; ± 2 days for Day 29)
9.	Received prohibited medication, as determined by the PI and agreed by the MM
10.	Causally related Grade 3 or higher unsolicited AE as assessed by the PI ^a
11.	Causally related SAE or potential AESI as assessed by the Sponsor

AE=adverse event; AESI = adverse event of special interest; IP=investigational product; MM = medical monitor; PI=principal investigator, SAE = serious adverse event

^aAny AE is considered to be related to the vaccine administration if assessed by the PI as being “possibly” or “probably” or “definitely” related.

7.3.2. Withdrawal from Study

Reasons for withdrawal of individual participants from the study prior to the Month 13 final safety follow-up phone call are to be recorded on the eCRF. The reason for withdrawal from the study will be recorded as one of the following:

1. Occurrence of any AE which, in the opinion of the PI or designee, warrants the participant’s permanent withdrawal from the trial (medical circumstances permitting, the participant will be encouraged to continue in the study for safety-only follow-up; refer to [Section 7.3.1](#)).
2. Death
3. Lost to follow-up (see [Section 7.4](#))
4. Noncompliance with study drug
5. Physician decision
6. Withdrawal (of consent) by the participant
7. Other (specify reason)

If the PI determines a participant has been noncompliant with study procedures, the PI will document the reason for noncompliance, and the participant will be withdrawn from the study.

The PI will notify Emergent promptly when a participant is withdrawn from the study. Before a participant who has received at least one vaccination is withdrawn from the study, the participant will be encouraged to comply with safety-only follow up procedures for the remaining study duration through Month 13 (refer to [Section 7.3.1](#)). An EWV will be requested of any participant who has received at least one vaccination but is withdrawn from the study before in-clinic visit Day 64 (refer to [Section 8.1.7](#) for EWV procedures).

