6.1.2. Dosing and Administration

The dosing schedule for each treatment group is presented in [Table 3](#).

Table 3: Dosing Schedule

Group Number/Treatment	Days 1 and 15	Day 29
1/AV7909 Lot 1	0.5 mL AV7909 IM	0.5 mL placebo SC
2/AV7909 Lot 2	0.5 mL AV7909 IM	0.5 mL placebo SC
3/AV7909 Lot 3	0.5 mL AV7909 IM	0.5 mL placebo SC
4/BioThrax	0.5 mL BioThrax SC	0.5 mL BioThrax SC

IM = intramuscular; SC = subcutaneous.

AV7909=0.5 mL AVA + 0.25 mg CPG 7909. Placebo=saline for injection.

All vaccinations will be administered in the clinic by authorized unblinded personnel following a complete or symptom-directed PE and (in WOCBP only) urine pregnancy test. If a participant has any condition that, in the opinion of the PI or designee, would render vaccination unsafe for that individual (eg, febrile illness, pregnancy) or would interfere with evaluations, then the vaccination will be rescheduled (if the condition is likely to resolve and the rescheduled vaccination visit will still occur within the visit window; refer to [Section 8.1](#)) or discontinued (refer to [Section 7.3.1](#)). Participants who fail for any reason to receive their first vaccination on the day of randomization will be withdrawn from the study and will be considered ineligible for study rescreening. Participants who fail to receive their second vaccination within the allowed visit window or for whom scheduling or other conflict precludes receipt of the third vaccination within the allowed visit window will be discontinued from further vaccinations. All vaccinated participants (regardless of number of injections) will continue to participate in the trial for all subsequent safety visits and follow-up phone calls.

Vaccinations will be administered in alternating arms (when possible) for each injection. For example, if the Day 1 injection is administered to the left arm, it is recommended that the Day 15 injection be administered to the right arm, and Day 29 injection be administered to the left arm. Using the same arm for subsequent vaccination(s) if necessary, may occur only in a case when the other arm is not available for vaccination and only if any sign(s) or symptom(s) of a prior injection have been resolved. The arm used for each injection must be recorded in the source documents and eCRF.

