8.3.5. Other Safety Assessments

8.3.5.1. E-Diary Reactogenicity

Reactogenicity (solicited systemic and injection site reactions) will be monitored by the site for 30 minutes after vaccination and thereafter assessed daily by the participants using e-diaries, starting on the evening after each vaccination, for at least seven days. Participants who do not have or don't want to use their personal electronics to access the web-enabled e-diary will be provided a hand-held device for purposes of this study, along with pre-paid return packaging to enable its return at the conclusion of all e-diary entries. Participants will also receive instructions on e-diary completion and be provided with an oral thermometer and injection site reaction

measurement tool on Day 1. Failure of a participant to comply with e-diary entry requirements will prompt compliance alerts being issued to the participant and to the clinical site, for site staff to follow up the noncompliance with the individual.

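### Protocol 7.3.2 requires study withdrawal for procedural noncompliance, conflicts with 6.1.2, 7.3 and 11.6, and leaves it unclear whether Month 13 safety follow-up continues

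*Protocol*

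**What the plan says.** Five places in the protocol bear on whether noncompliance ends a vaccinated participant's safety follow-up.

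- **7.3.2, Withdrawal from Study.** Once the PI has determined noncompliance with study procedures, "the PI will document the reason for noncompliance, and the participant will be withdrawn from the study". The next paragraph adds that before a vaccinated participant is withdrawn, "the participant will be encouraged to comply with safety-only follow up procedures for the remaining study duration through Month 13". The list of withdrawal reasons contains "Noncompliance with study drug" (reason 4) but no entry for noncompliance with procedures.
- **7.3, Individual Subject.** The PI can discontinue someone's participation "at any time if medically necessary or for reasons of noncompliance". For anyone vaccinated at least once, "Every attempt will be made to follow participants for safety for the entire duration of the trial through Month 13".
- **6.1.2, Dosing and Administration.** "All vaccinated participants (regardless of number of injections) will continue to participate in the trial for all subsequent safety visits and follow-up phone calls".
- **8.3.5.1, E-Diary Reactogenicity.** "Failure of a participant to comply with e-diary entry requirements will prompt compliance alerts being issued to the participant and to the clinical site", and the site then follows up with the individual. Withdrawal is not mentioned.
- **11.6, Protocol Deviations.** After a significant deviation, the PI and medical monitor decide jointly whether the participant continues in the trial.

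**The concern.** The 7.3.2 sentence is mandatory once the PI has made the judgement. It covers any study procedure, and noncompliance is not defined. Taken literally, it removes a person whom 6.1.2 keeps in.

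The endpoints at stake need little cooperation after Day 64. SAEs through the 12-month call are the primary safety endpoint (Protocol 3.2.1), and autoimmune AESIs over the same period are a secondary one (3.2.2). From Day 64 on, both are collected mainly by quarterly telephone call. A participant who neglects the diary or misses a clinic visit may still answer the telephone.

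If such a person is withdrawn, later events go unseen. Sites could also apply an undefined criterion differently.

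**Working it through.** **1. The passages side by side**

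| Section | Effect of noncompliance | Who decides |
|---|---|---|
| 7.3.2 | Withdrawal follows once noncompliance is determined | PI |
| 7.3 | Discontinuation is optional | PI |
| 6.1.2 | Vaccinated participants stay in safety follow-up; no exception stated | – |
| 8.3.5.1 (diary) | Alerts and site follow-up | – |
| 8.1.8 (missed interim call) | The next scheduled call is still attempted | – |
| 11.6 (significant deviation) | Case by case | PI and medical monitor |

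A site cannot apply 7.3.2 literally and also satisfy 6.1.2.

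**2. Does the encouragement paragraph settle it?** Only in part.

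- It places the encouragement before withdrawal, but does not say that a participant who accepts is no longer to be withdrawn.
- Section 7.3.1 counts a complying safety-only participant as continuing, but that sentence concerns people who stopped vaccination early. Someone who had all three injections and then lapses is not covered.
- Section 7.3.1 also keeps diary entries for past vaccinations mandatory in safety-only status, so moving to that status does not cure a diary lapse.
- Withdrawal reason 1 (AE) carries its own clause on continuing for safety-only follow-up. The noncompliance sentence has none.

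**3. What the analysis would do.** The Safety Population is everyone randomized and vaccinated at least once (SAP 3.2). SAEs and AESIs are summarized as simple proportions and relative risks (SAP 7.2.3, 7.2.4) on observed cases (SAP 4.4). An early-withdrawn participant stays in the denominator, and an event nobody hears about counts as no event. Because the reason list has no entry for procedural noncompliance, the disposition table (SAP 5.1) might not show how many such withdrawals occurred.

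**4. Follow-up lost per person.** On nominal days, withdrawal at Day 29 leaves 394 − 29 = 365 of 394 − 1 = 393 days unobserved (365/393 = 92.9%).

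**5. The plan's own figure.** Protocol 10.1: 3300 AV7909 participants, 10% drop-out, 3000 for safety, 95% probability of detecting an AE rate of 0.1%.

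P(at least one event) = 1 − (1 − 0.001)^n

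- n = 3000: 95.03%, so the stated figure reproduces.
- n = 3300 × 0.90 = 2970: 94.88%.

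**6. Extra loss.** The documents give no rate, so the range is assumed, taken beyond the 10% allowance, with each lost participant contributing nothing.

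| Assumed extra loss (of 3300) | n | P(at least one event) |
|---|---|---|
| 1% | 2937 | 94.7% |
| 2% | 2904 | 94.5% |
| 5% | 2805 | 94.0% |
| 10% | 2640 | 92.9% |

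This overstates the effect. The 10% allowance does not say which losses it covers, so these withdrawals may already be inside it. Withdrawn participants also contribute their observed time.

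**7. Relative risk, illustration only.** Suppose 5% of AV7909 and 2% of BioThrax participants were withdrawn at Day 29, with a constant event rate and no link between withdrawal and event risk. The observed relative risk would be the true one times (1 − 0.05 × 0.929)/(1 − 0.02 × 0.929) = 0.954/0.981 = 0.97. With equal withdrawal in both arms it would be unchanged. A link between withdrawal and event risk could do more, but the documents give nothing from which to size it.

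**The case against.** A reader might infer that Month 13 data are lost by rule. The documents do not support that.

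- Withdrawal depends on a PI judgement, and the same section directs sites to encourage safety-only follow-up first.
- The commonest lapses have their own handling, none of which withdraws anyone: diary failures (8.3.5.1), missed interim calls (8.1.8) and out-of-window vaccinations (6.1.2). A specific rule would normally prevail over a general one.
- Section 4.4 classifies people who miss the Month 13 contact as withdrawn; it does not forbid contact after noncompliance.
- Section 9.7.2 lists acceptable reasons to stop following an ongoing SAE or AESI, and noncompliance is not among them.
- SAP Appendix IV reports that four people who enrolled at two sites were terminated at the second but are being followed at the first to the end of study. A serious breach did not end their safety follow-up.

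A reader might also infer that the safety sample size is undermined, or that the loss biases the comparison between arms. Neither is shown. The change in detection probability is immaterial, and nothing in the documents links noncompliance withdrawal to reactogenicity or to arm.

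These points stand, and they reduce the matter to one of risk and consistency. They do not remove the contradiction. The intent to keep following people has to be assembled from other sections, while the sentence a site would consult on noncompliance says the opposite. Section 9.7.2 concerns events already under way, not new ones, and the duplicate enrollees are an unusual case.

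**Conclusion.** The concern holds as an internal inconsistency with an avoidable risk to the primary safety endpoint. Section 7.3.2 conflicts with 6.1.2, 7.3 and 11.6 on whether noncompliance ends participation, and its own next paragraph does not resolve the conflict. A site reading the sentence literally can end SAE and AESI collection for a willing participant.

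The number of participants affected is unknown. For each one withdrawn at Day 29, about 93% of nominal follow-up would be unobserved. Under assumed extra losses of 1% to 5%, the detection probability falls by less than one percentage point from 94.9%, so the case does not rest on power. Informative loss by arm is possible but undocumented. No figure in the plan is wrong on this point. The change is worth making because AESIs are expected to be rare, single unseen events matter, and the remedy is cheap.

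**What to change.** Reconcile the passages by replacing the 7.3.2 sentence with wording such as:

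*Noncompliance with study procedures is documented as a protocol deviation and is not by itself a reason to end safety follow-up; a vaccinated participant who is willing to be contacted remains in safety-only follow-up through Month 13.*

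Then align two places with it:

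- **7.3:** state that discontinuation by the PI for noncompliance does not by itself end safety follow-up of a vaccinated participant.
- **7.3.2, reason 4:** add a safety-only follow-up clause like the one reason 1 already has.

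Leave the other listed withdrawal reasons (AE, death, lost to follow-up, physician decision, withdrawal of consent, other) and the Table 5 vaccination rules unchanged. Procedural lapses will then appear in the deviation summary (SAP 5.2).

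The cost is a short amendment under Protocol Section 14, some extra call attempts to less cooperative participants, and more deviation records. No analysis or sample size changes.
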